# 4.2.3. Sensitivity analyses

Missing data sensitivity analyses using multiple imputation (MI) methods will be conducted for each of the co-primary endpoints to investigate the impact of missing data and to examine the robustness of the analyses of the primary endpoints to departures from the assumption that missing data are MAR. These analyses will use the same intercurrent event strategy as outlined for the primary estimand in Section 1.1.2. The MI methods are based on pattern-mixture models described by Carpenter [Carpenter, 2013]. The pattern-mixture model approach to sensitivity analysis models the distribution of a response as the mixture of a distribution of the observed responses and a distribution of the missing responses.

#### Sensitivity Analysis 1

For the first sensitivity analysis, participants with missing data at Week 52 who had taken their Week 26 dose of interventional product (and are therefore considered on-treatment at Week 52) will have missing data imputed under the assumption of MAR. Participants with missing data at Week 52 who had not taken their Week 26 dose of interventional product (and are therefore considered off-treatment at Week 52) will have their monotone missing data (i.e. after their final non-missing time point) imputed using a jump to reference (J2R) approach. Implementation of the J2R method assumes that for

participants in the experimental treatment group (Depemokimab) with missing data, their imputed mean response is that of the reference treatment group (Placebo).

Multivariate normal models will be fitted using a Markov Chain Monte Carlo (MCMC) approach. The covariates will be the same as for the primary analysis. The independent samples drawn from the posterior distributions for the mean and variance-covariance matrix provide input into the imputation model. For each participant with missing data, these sampled values of the parameters for mean vectors and the variance-covariance matrices specify a joint distribution for their observed and unobserved outcome data. Under the J2R approach, the mean estimate is constructed using the estimated beta associated with the reference treatment, as well as the participant's other covariates.

For each participant with missing data, this joint pattern-specific distribution can be used to construct the conditional distribution of their missing data given their observed data. The missing data is sampled once from this distribution to create a single dataset for each imputation. Together these form a series of complete imputed datasets for each of the primary endpoints (with imputed data under either MAR or J2R).

Each imputation dataset will be analyzed using the same methodology as for the primary analysis and the results from each analysis of each sample will then be combined using Rubin's method [Rubin, 1987] as implemented in PROC MIANALYZE in SAS.

Results presentation will be the same for the co-primary analyses described in Section 4.2.2 for the EOS visit / time period. Additionally, for each of the co-primary endpoints, for the EOS visit / time-period only, a forest plot will be produced to present the estimated treatment differences and 95% CIs for the primary estimand using FAS, the supplementary estimand using FAS, the primary estimand using FAS-Modified, and the J2R approach.

#### Sensitivity Analysis 2

An additional tipping point sensitivity analysis will explore the impact of missing data by using differing assumptions regarding the endoscopic NP score at Week 52 and the nasal obstruction VRS at Weeks 49-52 in subjects who withdraw from the study. Subjects who withdraw from study early will have missing data imputed for the period of time between withdrawal from the study to the Week 52 visit / Week 49 – 52 time period based on a range of values for the mean NP score / mean nasal obstruction VRS following study withdrawal. Assumptions about missing values on the treatment arm and placebo arm will vary independently, and will include scenarios where participants with missing data in the active arm have worse outcomes than participants with missing data in the placebo arm. This analysis will allow for determination of 'tipping point(s)' of the values for missing data that would cause a change in the statistical significance of the result of the treatment comparison.

As a first step, participants with missing data will have missing data imputed under the assumption of MAR. For each treatment group, the imputed values will vary separately by a value of delta, where delta represents a change in endoscopic NP score / mean nasal obstruction VRS over a 4-week interval. The deltas investigated will cover a range that is plausible for the respective endpoint under the MAR assumption. For NP score, the deltas evaluated will range from -8 to 8 by 0.5 increments. For nasal obstruction VRS, the deltas

evaluated will range from -1.5 to 1.5 in 0.25 increments. The final range and increment of deltas will be investigated on final data and may be adjusted to ensure it supports a meaningful tipping point range.

The tipping point multiple imputation method will be based on pattern mixture models [Keene, 2014]. Each imputation dataset will be analyzed using the same methodology as for the primary analysis and the results from each analysis of each sample will then be combined using Rubin's method [Rubin, 1987] as implemented in PROC MIANALYZE in SAS.

A table of p-values for each treatment comparison made across the range of imputed values (deltas) for each respective endpoint will be presented. Graphics depicting treatment difference and non-significant vs. significant surfaces will be produced for the range of imputed values (deltas) for each respective endpoint.

The seeds for all planned MI sensitivity analyses will be '217095'.

## 4.3. Secondary Endpoints Analyses

## 4.3.1. Definition of endpoints

The secondary endpoints are:

- Change from baseline in mean symptom score for rhinorrhoea (runny nose) VRS from Week 49 through to Week 52
- Change from baseline in mean symptom score for loss of smell VRS from Week 49 through to Week 52
- Change from baseline in Lund Mackay (LMK) CT score at Week 52
- Change from baseline in SNOT-22 total score at Week 52
- Change from baseline in mean nasal obstruction score VRS from Week 21 through to Week 24
- Change from baseline in total endoscopic NP score at Week 26

The VRS endpoints collected daily in the morning via the eDiary will be handled in the same way as the co-primary VRS endpoint, with daily data being collapsed into 4-week time periods as described in Section 6.3.4.2. A CDF plot will also be provided for the change from baseline by treatment group for the endpoints: (1) Change from baseline in mean symptom score for rhinorrhoea (runny nose) VRS from Week 49 through to Week 52 and (2) Change from baseline in mean symptom score for loss of smell VRS from Week 49 through to Week 52.

A computed tomography (CT) scan is performed at Visit 16 (Week 52) and all image recordings of CT scans will be sent to an independent reviewer for centralized blinded data assessment. The central reading for LMK scoring will be used for analysis. The LMK CT scoring system is based on localization with points given for degree of opacification: 0 = normal, 1 = partial opacification, 2 = total opacification. These points are applied to the maxillary, anterior ethmoid, posterior ethmoid, sphenoid, frontal sinus

on each side. The osteomeatal complex (OC) is graded as 0 = not occluded, or 2 = occluded deriving a maximum score of 12 per side. The combined score will range from 0-24 with higher scores indicating greater disease severity. Non-missing scores must be available for all portions on both sides for the combined score to be calculated; otherwise the score will be set to a value of 9 to indicate a missing or unreadable value.

SNOT-22 is a 22-item questionnaire that will be completed at each of the scheduled clinic visits using the eDiary. Participants will be asked to rate the severity of their condition on each of the 22 items over the previous 2 weeks using a 6-point rating scale of 0-5 including: 0 = Not present/no problem; 1 = Very mild problem; 2 = Mild or slight problem; 3 = Moderate problem; 4 = Severe problem; 5 = Problem as "bad as it can be". The total score range for the SNOT-22 is 0-110, where higher scores indicate greater disease impact. All questions must be answered to generate an overall score; if any individual questions are missing then the overall score will be missing.

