# 2.1. Multiplicity Adjustment

The hypotheses to be tested are structured as shown in Figure 1. The co-primary endpoints will be tested first and if these comparisons are both significant at the 2-sided 5% level, testing will continue for the secondary endpoints within the study according to the testing procedure detailed in Figure 1. Testing of secondary endpoints will be carried out in a hierarchical manner, dependent on statistical significance having been achieved for the previous endpoint in the hierarchy. Other pairwise comparisons will be performed but are not part of the multiple testing strategy. Analyses of other efficacy measures are nested under the secondary efficacy measures and no multiplicity adjustment is planned for these other efficacy endpoints. The analyses for these other efficacy endpoints and some of the earlier time points for some of the co-primary and secondary endpoints are not adjusted for multiplicity and so nominal significance will be evaluated in a descriptive manner with these analyses using a 5% reference level.

A pre-specified pooled analysis of data from the ANCHOR-1 and ANCHOR-2 studies is planned for the secondary endpoints of time to first nasal surgery (actual or entry on waiting list) or disease-modulating medication for CRSwNP, time to first nasal surgery (actual) or disease-modulating medication for CRSwNP, proportion of participants requiring at least 1 course of systemic corticosteroids or disease-modulating medication for CRSwNP or nasal surgery (actual), and change from baseline in ACQ-5 score in participants with an ACQ score of >0.75 at baseline. This pooled analysis will be carried out after statistical significance is achieved for both co-primary endpoints within both studies. The closed-testing manner for the pre-specified pooled hierarchy is described further in the pooled SAP.

Figure 1 Conceptualization of Statistical Testing Strategy Across Studies ANCHOR-1 and ANCHOR-2

Note: Endpoint names in Figure 1 are abbreviated. Refer to Section 1.1 for full nomenclature of endpoints.

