#### 4.1.2. Baseline Definition

For all visit-based endpoints, including the co-primary endpoint of endoscopic NP score, baseline will be defined as the latest non-missing measurement collected prior to the first dose of study treatment. This will generally be from the Day 1 (Visit 2) assessment but may be from an unscheduled or screening assessment. In the case a visit-based assessment was collected after the first dose of study treatment, but still on the day of the randomization visit on Day 1 (Visit 2), then that assessment may be used.

For daily efficacy endpoints collected in the eDiary, baseline will be the average score from the 28 calendar days up to and including the date of randomization. This means the average will be based on the non-missing data from Day -27 to Day 1 inclusive. There must be a minimum of 4 non-missing values from Day -6 to Day 1 inclusive in order to derive the baseline, otherwise it will be set to missing.

Unless otherwise stated, if baseline data is missing no derivation will be performed and baseline will be set to missing.

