# 4.2. Primary Endpoints Analyses

#### 4.2.1. Definition of endpoints

The co-primary endpoints are:

- a) Change from baseline in total endoscopic NP score at Week 52 (centrally read)
- b) Change from baseline in mean nasal obstruction score (verbal response scale [VRS]) from Week 49 through to Week 52

The total endoscopic NP score is assessed in the clinic at visits 2, 5, 7, 9, 11, 13, 15 and 16, or early withdrawal visit (weeks 0, 12, 20, 26, 32, 40, 48 and 52). The score is then graded by independent reviewers at a central lab who are blinded to treatment. The total score is reported as the sum of the right and left nostril scores and ranges from 0 to 8, with higher scores indicating greater disease severity. Non-missing scores must be available for both sides for the combined score to be calculated; otherwise the score will be set to a value of 9 to indicate a missing or unreadable value.

The nasal obstruction VRS score will be collected daily in the morning via the eDiary. Each day the participant will indicate the severity of their symptoms giving a score ranging from 0 to 3, with the 4 options indicating no symptoms, mild symptoms, moderate symptoms, and severe symptoms. The daily data will be collapsed into thirteen 4-week time periods, with the value for each time period based on the average of the non-missing days covered by that time period as described in Section 6.3.4.2. For each 4-week time period the average will only be derived if there are non-missing values for at least 4 days out of 7 in at least 3 out of 4 weeks, with at least 15 minimum values, otherwise it will be set to missing.

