# **Model Specification**

 Statistical analyses for the change from baseline in Lund Mackay CT score at Week 52 will be performed using an analysis of covariance (ANCOVA) model with covariates of treatment group, baseline score, log(e) baseline blood eosinophil count, region and previous surgery for nasal polyps.

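### The SAP codes an incomplete Lund-Mackay CT total as 9, a valid score on its 0–24 scale, and gives no step to tell the two apart

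*SAP*

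**What the plan says.** SAP Section 4.3.1 builds the Lund-Mackay total from five sinuses per side, each scored 0, 1 or 2, and an osteomeatal complex per side scored 0 or 2. It then states: "The combined score will range from 0-24 with higher scores indicating greater disease severity". The next sentence requires all portions to be scored "on both sides for the combined score to be calculated; otherwise the score will be set to a value of 9 to indicate a missing" result, or one that cannot be read.

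Two neighbouring scores are handled differently in effect:

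- **Endoscopic NP score (SAP 4.2.1).** The rule has almost the same wording: scores "must be available for both sides for the combined score to be calculated; otherwise the score will be set to a value of 9". That total is the "sum of the right and left nostril scores and ranges from 0 to 8, with higher scores indicating greater disease severity", so 9 cannot be a real value.
- **SNOT-22 (SAP 4.3.1).** No numeric code is used: "if any individual questions are missing then the overall score will be missing".

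In SAP 4.3.2, the change-from-baseline analysis for "Lund Mackay CT score at Week 52 will be performed using an analysis of covariance (ANCOVA) model with covariates of treatment group, baseline score" and further terms. For visit-based endpoints, SAP 4.1.2 says "baseline will be defined as the latest non-missing measurement collected prior to the first dose of study treatment".

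**The concern.** A missing-value code works only if no real observation can take that value. Here it can. Once a 9 is stored as the total, nothing in that variable shows whether it was measured or assigned. The analysis text in SAP 4.3.2, the baseline rule and the derivation appendix (SAP 6.3) contain no step that recodes, excludes or flags a coded 9. The gap affects the Week 52 outcome, the baseline covariate and the summary statistics.

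The endpoint carries weight. Secondary testing is "dependent on statistical significance having been achieved for the previous endpoint in the hierarchy" (SAP 2.1). In the order of Protocol Figure 4, Lund-Mackay comes third and gates SNOT-22, nasal obstruction at Weeks 21–24 and NP score at Week 26. An error here could therefore carry into three further confirmatory tests.

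**Working it through.** **Step 1: the plan's range, and whether 9 is attainable.** The inputs are the component scales in SAP 4.3.1 and Protocol Appendix 9. One side has 3⁵ × 2 = 486 patterns. The numbers of patterns giving side totals 0 to 12 are 1, 5, 16, 35, 60, 81, 90, 81, 60, 35, 16, 5, 1. Two sides give 486² = 236,196 patterns. Totals run from 0 to 24, which reproduces the SAP's range, and every integer is attainable. Patterns totalling 9:

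2 × (1×35 + 5×60 + 16×81 + 35×90 + 60×81) = 2 × 9,641 = 19,282.

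That is 8.2% of patterns. It shows that 9 is attainable; it is not a patient frequency. For the NP score the maximum is 8, so 9 has no overlap.

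**Step 2: if every 9 is deleted.** The documents give no Lund-Mackay mean or SD, so a normal total was assumed with means 12 to 20 and SDs 4 to 6. The share of true 9s is P(8.5 < X < 9.5). At mean 17, SD 5 this is Φ(−1.5) − Φ(−1.7) = 2.2%. Over the grid it runs from 0.2% (mean 20, SD 4) to 7.5% (mean 12, SD 4). With the SAP's 118 evaluable participants per arm, that is 0.3 to 8.9 valid scores lost per arm.

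**Step 3: if coded 9s are analysed as scores.** If a fraction f of Week 52 totals is coded and their true mean is m, the arm mean shifts by f × (9 − m). With f = 5% and m = 17 the shift is 0.05 × (−8) = −0.40. With equal f in both arms, the treatment difference is multiplied by (1 − f).

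An ANCOVA simulation put this into test terms: 5,000 runs per case, 118 per arm, baseline mean 18, SD 5, correlation 0.5, scores rounded and clipped to 0–24. The 5% rate is borrowed from the general non-evaluable allowance in SAP Section 5; it is not a rate of unreadable scans. Mean 17, SD 5 applies unless stated.

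| Coded 9 (active vs placebo) | Assumed effect | Estimate | Rejection rate |
|---|---|---|---|
| 5% vs 5% | 0 | −0.001 | 5.2% |
| 5% vs 5% | −2 | −1.78 | 87.6% |
| same, set to missing | −2 | −1.88 | 91.7% |
| same, all 9s dropped | −2 | −1.84 | 90.6% |
| 5% vs 0% | 0 | −0.39 | 10.2% |
| 0% vs 5% | 0 | +0.39 | 11.3% |
| 5% vs 0%, mean 12, SD 5 | 0 | −0.15 | 5.8% |
| 5% vs 0%, mean 20, SD 4 (baseline mean 20) | 0 | −0.53 | 21.0% |

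At correlations 0.3 and 0.7, the 5% vs 0% case at mean 17 gives type I error of 10.2% and 13.2%. A separate 3,000-run repeat of the main cases agreed: −0.39 and 10.2%; 5.1% at equal rates; power 87.8% against 91.6%.

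Small imbalances matter little. Under no true effect, 1% vs 0% gives −0.09 and 5.2%, and 2% vs 1% gives −0.07 and 5.3%. With 1% in both arms and an effect of −2, power is 91.4% if coded 9s are analysed and 93.6% if they are set to missing.

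**The case against.** The best reply is that the SAP says what the 9 is for. An analyst who entered it as a severity score would be departing from the plan, so the cases in Step 3 describe a programming error. The derivation rule also tests the components, so whoever applies it knows at that moment which totals were assigned. Protocol 8.2.3 tells the reader to score the former osteomeatal complex where earlier surgery removed it, which closes one likely source of incomplete totals. Reading is central and blinded, so unequal rates are not expected. A Programming Specification, not available here, may contain the missing step.

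Much of this stands. The intent is clear, the components could separate the two kinds of 9, and the large type I errors need an imbalance that the documents give no reason to expect. None of it repairs the rule. Intent does not show which stored 9s are codes, and the SAP does not say that the components will be used to find them. The SAP cites the Programming Specification for displays, regional outputs and unscheduled visits, not for this derivation. A correct step there would still leave the SAP clause wrong.

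**Conclusion.** The point holds. The code lies inside the valid range, and no stated step separates coded from true values. This is a rule that is wrong as written, not merely a missing detail, and it concerns a secondary endpoint under type I error control. It should be corrected, although it does not show that the trial is biased.

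The overlap itself needs no assumption. Its effect on results is unknown, because the documents give no Lund-Mackay mean, SD or rate of incomplete scans. Under the assumptions above, equal rates cost some power and do not inflate type I error. Unequal rates could bias the difference in either direction. Deleting all 9s would lose between a fraction of one and about nine valid scores per arm.

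**What to change.** Replace the final clause of the Lund-Mackay rule in SAP 4.3.1 with a statement that an incomplete combined score, at baseline or Week 52, is set to missing. If the central reader needs a code in the raw data, choose one outside 0–24 and state that it is excluded from baseline, change from baseline and the ANCOVA.

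The NP score code can stay. The worst-value rule after surgery or disease-modulating medication is unaffected, as are sample size and alpha.

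The cost is one SAP clause and one line in the derivation specification, with no new data. Participants with an incomplete CT total drop out of this single-timepoint ANCOVA, as a missing flag already implies.

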## 4.3.2. Main analytical approach

Change from baseline in LMK CT score at Week 52 will be analyzed as described below. All other secondary endpoints will be analyzed in the same way as the co-primary endpoints. Summary statistics will be produced for each visit/4-week time-period by treatment group for each secondary endpoint. The same secondary endpoints analyses will be performed using the FAS-Modified analysis set as an additional analysis.

# **Model Specification**

 Statistical analyses for the change from baseline in Lund Mackay CT score at Week 52 will be performed using an analysis of covariance (ANCOVA) model with covariates of treatment group, baseline score, log(e) baseline blood eosinophil count, region and previous surgery for nasal polyps.

## **Model Checking & Diagnostics**

- The Kenward-Roger (KR) method [Kenward, 1997] for approximating the denominator degrees of freedom and correcting for bias in the estimated variance-covariance of the fixed effects will be used in the analyses. This will be achieved by specifying the DDFM=KR option in the MODEL statement within PROC MIXED.
- Appropriate graphs will be reviewed as part of the model checking process to ensure that
  distributional assumptions hold. These will include a normal probability plot of the residuals
  and a plot of the residuals versus the fitted values (checking the normality assumption and
  constant variance assumption of the model, respectively).

#### **Model Results Presentation**

 The adjusted mean change from baseline with corresponding standard error for each treatment group will be presented. The estimated treatment difference will be presented together with 95% confidence interval (CI) for the difference and p-value for the inequality comparison.

For the co-primary endpoints and the secondary endpoints for the EOS visit/time-period only, a forest plot will be produced to present the estimated treatment differences and 95% CIs.

# 4.4. Other Endpoints Analyses

#### 4.4.1. Definition of endpoints

The other endpoints are:

- Change from baseline in mean overall symptom VAS) score from Week 49 through to Week 52
- Achieving a one point or greater decrease from baseline in NP Score at Week 52 without first having nasal surgery (actual) or disease-modulating medication for CRSwNP
- Change from baseline in mean individual symptom (VRS) score for facial pain from Week 49 through to Week 52
- Change from baseline in mean individual symptom (VRS) score for mucus in throat from Week 49 through to Week 52
- Change from baseline in the mean nasal polyps symptoms composite score (combining VRS scores for nasal obstruction, rhinorrhoea (runny nose), loss of smell, and mucus in throat) from Week 49 through to Week 52
- Change from baseline in mean CRS symptoms and facial pain composite score (combining VRS scores for nasal obstruction, rhinorrhoea (runny nose), loss of smell, and facial pain) from Week 49 through to Week 52
- Achieving a meaningful decrease from baseline in their mean individual symptoms VRS and composite VRS from Week 49 through to Week 52 without first having nasal surgery (actual) or disease-modulating medication for CRSwNP.
  - o Further details on meaningful decrease for each individual symptom VRS and composite VRS are described in Section 4.4.2
- Achieving an 8.9-point or greater decrease from baseline in SNOT-22 total score at Week 52 without first having nasal surgery (actual) or disease-modulating medication for CRSwNP
- Achieving a 28-point or greater decrease from baseline in SNOT-22 total score at Week 52 without first having nasal surgery (actual) or disease-modulating medication for CRSwNP
- Change from baseline in SF-36 Mental Component Summary (MCS) score, Physical Component Summary (PCS) score and eight domains at Week 52
- Change from baseline in WPAI-GH scores at Week 52

The overall visual analogue scale (VAS) symptoms score will be collected daily in the morning via the eDiary. Participants will be asked to rate their overall symptoms at their worst over the previous 24 hours. A scale from 0 (None) to 100 (As bad as you can imagine) will be used. The final VAS scores that are reported will be derived from the electronically captured score by dividing each score by 10 and will range between 0 and 10. This endpoint will be handled in the same way as the co-primary VRS endpoint, with daily data being collapsed into 4-week time periods as described in Section 6.3.4.2.

A nasal obstruction VAS score will also be collected daily in the morning via the eDiary at key time-periods during the study. The data from this endpoint will be collapsed into the expected time periods as described in Section 6.3.4.2.

The VRS composite scores will be derived for each day by taking the mean of the individual VRS scores for that day. All of the individual VRS scores contributing to a composite score must be non-missing in order to derive the mean.

All VRS endpoints will be handled in the same way as the co-primary VRS endpoint, with daily data being collapsed into 4-week time periods as described in Section 6.3.4.2.

The short-form-36 (SF-36) questionnaire consists of 36 self-administered questions that cover 8 health domains: physical functioning (PF), role physical (RP), bodily pain (BP), and general health (GH), vitality (VT), role emotional (RE), social functioning (SF), and mental health (MH) with a recall of 4 weeks. Certified scoring of the SF-36 survey will be performed using OPTUM TM software. The 8 domain scores are provided by the software. Scale scores range from 0 to 100 where higher scores indicate better quality of life.

The work productivity and activity impairment (WPAI) questionnaire is an instrument to measure impairment in paid and unpaid work and daily activities. Six questions will be collected at each visit including employment status, hours missed from work due to health problems and due to other reasons, hours actually worked, and how much health problems affected productivity and activity.

The following measures will be derived from the 6 WPAI-GH questions ranging from 0 (no impairment) to 100 (full impairment):

Derived Outcomes Derivation	Derived Outcomes Derivation
Work time missed due to health (%)	100 * Q2 / (Q2+Q4)
Impairment while working due to health (%)	10 * Q5
Overall work impairment due to health (%)	100* Q2 / (Q2 + Q4) + [(1 - (Q2 / (Q2+Q4))) x
	(Q5 / 10)]
Activity impairment due to health (%)	10 * Q6

Note (each question with a recall of 7 days):

- Q1 = Currently Employed
- Q2 = Time (hours) missed from work due to health problems during the past seven days
- Q3 = Time (hours) missed from work due to other reasons during the past seven days
- Q4 = Time (hours) actually worked during the past seven days
- Q5 = Productivity affected by health problems while working during the past seven days
- Q6 = Ability to do regular daily activities affected by health problems during the past seven days

Participants not currently employed will only answer Q6. Participants who answer 0 to Q4 will not answer Q5.

If any of the responses used to derive a score are missing or if a participant is not currently employed then the relevant score (work time missed, impairment while working, overall work impairment) will be set to missing.

For those who missed work and did not actually work in the past seven days, the percent overall work impairment due to health will be equal to the percent work time missed due to health.

For SF-36 and WPAI-GH, the intercurrent event of surgery and initiation of a disease-modulating medication for CRSwNP will be handled under the composite strategy by assigning participants their worst observed score prior to the event. All other intercurrent events described under the primary estimand strategy in Section 1.1.2 will be handled using a treatment policy strategy.

For all responder endpoints, participants who undergo nasal surgery or initiate a disease-modulating medication for CRSwNP will be included in the analysis as non-responders for all time points following the event, whichever occurred first. For participants with missing baseline data, a responder status will not be derived. Participants with missing data at a particular post-baseline visit / timepoint will be treated as non-responders for that visit/ timepoint. All other intercurrent events described under the primary estimand strategy in Section 1.1.2 will be handled using a treatment policy strategy.

